[Part 4 of 4 of the document. The other parts are not shown.]

The Investigator or designee must explain to each subject, before enrollment into the study, that for evaluation of study results, the subject's protected health information obtained during the study may be shared with the study Sponsor, regulatory agencies, and IRB/IEC/REB. It is the Investigator's (or designee's) responsibility to obtain written permission to use protected health information per country-specific regulations, such as the Health Insurance Portability and Accountability Act (HIPAA) in the US, from each subject. If permission to use protected health information is withdrawn, it is the Investigator's responsibility to obtain a written request, to ensure that no further data will be collected from the subject and the subject will be removed from the study.

9.3.3.1 Study Safety Evaluation Criteria

If any of the following events occur in a subject in the study who has received BMN 270 infusion, enrollment into the trial will be put on halt to complete an extensive safety analysis per Section 9.1.

- A 5-fold increase from baseline in ALT after BMN 270 administration
- The occurrence of Grade 3 or higher adverse events assessed as related to study drug, including liver failure and clinical hepatitis
- Grade 2 adverse event assessed as related to study drug that persists for at least 7 days
- The detection of neutralizing antibodies to hFVIII following BMN 270 infusion
- The persistent detection of the AAV vector genome in the semen of a participant more than 26 weeks after BMN 270 infusion, as discussed in Section 9.7.8.5
- The occurrence of a malignancy excluding skin cancers at any point after BMN 270 infusion

9.3.4 Subject Identification and Replacement of Subjects

Each subject will be assigned a unique subject identifier. This unique identifier will be on all CRF pages. In legal jurisdictions where use of initials is not permitted, a substitute identifier will be used.

Subjects who withdraw from the study will not be replaced.

9.3.5 Duration of Subject Participation

The duration of this study will be approximately 264 weeks. This includes 4 weeks of screening, 1 day of BMN 270 infusion, 16 weeks of Post-Infusion Follow-Up, and 244 weeks of Safety Follow-Up. A primary endpoint analysis on safety and efficacy will be performed at 16 weeks.

9.4 Treatments

BioMarin or its designee will provide the study site with study drug sufficient for study completion. BioMarin is responsible for shipping study drug to clinical sites.

9.4.1 Treatments Administered

BioMarin and/or its designee will provide the study site with a supply of IP sufficient for the completion of the study.

9.4.2 Identity of Investigational Product

9.4.2.1 Product Characteristics and Labeling

BMN 270 is a sterile, clear, colorless-to-pale yellow solution for IV infusion and is supplied in a 2 mL polypropylene cryovial. Each vial contains 1.1 mL of AAV5-hFVIII-SQ at a concentration of 2E13 vector genomes per mL in a pH 7.4 phosphate buffer.

The study drug label includes the following information: lot number, required storage conditions, a precautionary statement, expiry date, study number, and BioMarin name and address. Labelling will be done according to country specific requirements.

9.4.3 Storage

At the study site, all IP must be stored under the conditions specified in the IB in a secure area accessible only to the designated pharmacists and clinical site personnel. All IP must be stored and inventoried and the inventories must be carefully and accurately documented according to applicable state, federal and local regulations, ICH GCP, and study procedures.

9.4.4 Directions for Administration

After a physical exam performed by the PI or designee, participants will be admitted on the day of BMN 270 infusion. An IV catheter will be inserted into a suitable peripheral vein (e.g. the median cubital vein) and flushed with saline. FVIII replacement therapy will not be given since venipuncture is a minimally invasive procedure in these individuals under ordinary conditions.

BMN 270 will be prepared and infused as a pure solution over a dose-dependent time. Prepared drug will be kept at room temperature prior to administration. An electric syringe pump will be used to infuse through an in-line, low protein binding 0.22 micron filter. BMN 270 will be infused through the catheter using an appropriate infusion pump at a constant rate of 4 ml/min while monitoring the vital signs (pulse, blood pressure, respiration rate and temperature) at 15 minute (\pm 5 minutes) intervals. The anticipated maximum interval from initiation of thawing of BMN 270 to completion of the infusion is 4 hours, although the IP has been shown to be stable at room temperature for 6 hours.

Following completion of the infusion, vital signs will be monitored hourly (± 5 minutes) for 6 hours and then every 2 hours (± 15 minutes) for 6 hours and then at 4 hour intervals. If the vital signs are stable the catheter will be removed 20-24 hours after the infusion. Hemostasis at the puncture site will be established by applying pressure according to standard protocol for infusing FVIII concentrates. Subjects will remain in the clinic for 24 hours to observe for any immediate toxicity of the procedure. After 24 hours, participants will be discharged from the clinic unless toxicity has been observed in which case the stay in the clinic may be extended or the subject may transfer to a separate facility based on the evaluation and judgment of the Principal Investigator after consultation with the Medical Monitor.

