9.4.6.2 Selection of Dose for Each Subject

The starting dose was determined by expression of hFVIII observed in mice and monkeys and a scale up factor based on previous experience, an improved purification process over previous trials (thus potentially decreasing the risk of immune response), and a new evaluation of the titer (PCR performed after hairpin removal).

Approximately three weeks after an injection, the decision to escalate to the next dose level will be made based on the review of safety parameters and FVIII activity by the Sponsor and the DRB.

Subject 1 (Cohort 1) will be dosed by intravenous infusion with 6E12 vg/kg of body weight. If the FVIII activity level does not reach 5 IU/dL or greater (expressed as % in Figure 9.1.1) at the Week 3 visit in both assays, then no further subjects will be dosed in Cohort 1 and enrollment into Cohort 2 will initiate with Subject 2 at the next dose (2E13 vg/kg).

If the FVIII activity level in the first subject treated in Cohort 2 does not reach \geq 5 IU/dL at the Week 3 visit in both assays, then no further subjects will be dosed in Cohort 2 and enrollment into Cohort 3 (6E13) will initiate with the next subject.

If the FVIII activity level in the first subject treated in Cohort 3 does not reach \geq 5 IU/dL at the Week 3 visit in both assays, then the DRB will recommend whether to continue to add subjects to the cohort and/or whether to continue the study.

For the first subject treated in each Cohort, if the activity level reaches \geq 5 IU/dL and no safety issue is found, then up to four subjects will be enrolled in the Cohort. Although the optimum design of this study is three cohorts of 4 subjects, the adaptive nature of this trial allows the DRB to recommend allocating subjects to the cohorts based on activity levels of FVIII and safety signals.

Refer to Figure 9.1.1 for a visual representation of the study design.

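### At the Cohort 1 starting dose the infusion ends in about 4–8 minutes, so the 15 (±5) minute vital-sign rule yields no reading during infusion, and no end-of-infusion reading is listed

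*Protocol*

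**What the plan says.** All references are to the Amendment 3 text.

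- **Product and rate.** Section 9.4.2.1 supplies the vector "at a concentration of 2E13 vector genomes per mL". Under Section 9.4.4 it is "infused as a pure solution over a dose-dependent time", and it runs "at a constant rate of 4 ml/min while monitoring the vital signs" every 15 (±5) minutes. No infusion duration is stated for any cohort.
- **Starting dose.** Section 9.4.6.2 says Subject 1 "will be dosed by intravenous infusion with 6E12 vg/kg of body weight". If FVIII activity stays below 5 IU/dL in both assays at Week 3, "then no further subjects will be dosed in Cohort 1". If the first subject reaches the threshold with no safety issue, "then up to four subjects will be enrolled in the Cohort".
- **Vital-sign schedule.** Sections 9.7.8.4 and 12.4 require a reading before infusion and then every 15 (±5) minutes during it. The Table 9.1.1 footnote, visible here only through the Section 24 amendment table, says the same. Afterwards, Section 9.4.4 states: "Following completion of the infusion, vital signs will be monitored hourly" (±5 minutes) for 6 hours, then every 2 hours for 6 hours, then every 4 hours. None of these places lists a reading at the end of infusion or a shorter interval for Cohort 1.
- **Observation.** Section 9.4.4 also provides: "Subjects will remain in the clinic for 24 hours to observe for any immediate toxicity of the procedure".

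**The concern.** The protocol plainly intends vital signs to be taken while the vector is running in. A fixed rate, a fixed concentration and a dose per kilogram together determine how long the infusion lasts. At the lowest dose that is shorter than the monitoring interval, so a site following the text exactly would record nothing during the infusion in the first people ever given the product.

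The post-infusion schedule does not clearly close the gap. An hourly series after completion can begin at 0 h or at +1 h, and the text does not choose. On the +1 h reading, the period in which an acute infusion reaction is most likely to be looked for has no scheduled vital signs.

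Section 9.7.8 names vital signs as a safety variable. In-infusion values would exist for Cohorts 2 and 3 but not for the starting dose they would be compared with.

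The two provisions appear not to have been reconciled. Section 9.4.4 of Amendment 2 already had the 15-minute interval but no fixed rate; Amendment 3 added the rate.

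**Working it through.** The protocol states no infusion duration, so there is no figure of its own to reproduce.

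**Inputs**
- Concentration: 2E13 vg/mL, undiluted (Sections 9.4.2.1 and 9.4.4)
- Rate: 4 mL/min, constant (Section 9.4.4)
- Doses: 6E12, 2E13 and 6E13 vg/kg (Section 9.4.6.2)
- First in-infusion reading: 15 ± 5 min, so 10 min at the earliest (Sections 9.4.4, 9.7.8.4 and 12.4)
- Body weight: not given in the document; 50–110 kg is assumed, with 70 kg as the central value

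**Formulas**
- Volume (mL) = dose × weight / 2E13
- Duration (min) = volume / 4

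| Cohort | mL/kg | 50 kg | 70 kg | 110 kg |
|---|---|---|---|---|
| 1 (6E12) | 0.3 | 15 mL, 3.75 min | 21 mL, 5.25 min | 33 mL, 8.25 min |
| 2 (2E13) | 1.0 | 50 mL, 12.5 min | 70 mL, 17.5 min | 110 mL, 27.5 min |
| 3 (6E13) | 3.0 | 150 mL, 37.5 min | 210 mL, 52.5 min | 330 mL, 82.5 min |

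**Weight at which a Cohort 1 reading becomes possible**
- Early edge of the window: 10 min × 4 mL/min = 40 mL; 40 / 0.3 = 133 kg
- Nominal 15 min: 15 × 4 = 60 mL; 60 / 0.3 = 200 kg

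The result therefore does not depend on the exact weight range assumed.

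**Other cohorts**
- Cohort 2: the window opens before the infusion ends across the assumed range, but the nominal 15-minute point falls after the end below 60 mL / 1.0 mL/kg = 60 kg. At 70 kg one reading falls due.
- Cohort 3: the rule works as intended. At 70 kg three readings fall due, at 15, 30 and 45 minutes.

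**Time from infusion start to the next scheduled Cohort 1 reading**
- Hourly series starting at +1 h (±5 min): from 55 + 3.75 = 58.75 min to 65 + 8.25 = 73.25 min
- Hourly series starting at 0 h: nominally 3.75–8.25 min

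**Readings already scheduled after infusion, if the first is at +1 h**
- 6 (hours 1–6) + 3 (hours 8, 10, 12) + 3 (hours 16, 20, 24) = 12 over 24 hours

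**The case against.** The strongest reply is that an hourly series tied to completion of the infusion can naturally begin at completion. On that reading there is a value 4–8 minutes after the start and nothing is missing. That reading is possible but not written, and sites could reasonably go either way. The 59–73 minute figure is conditional on the +1 h reading. The absence of an in-infusion reading is not.

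It can also be said that one interval for three cohorts with different infusion times is a legitimate choice, and that the protocol promises no minimum number of in-infusion readings. That is true, so this is not a contradiction in the text. It is still a monitoring rule that produces no data at one of the three planned doses.

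The safeguards are real. There is a pre-infusion reading, adverse events are assessed at the infusion visit, the catheter is removed at 20–24 hours only if vital signs are stable, and the subject stays in the clinic for 24 hours. Cohort 1 is also the lowest dose, with a stated 10-fold margin from the mouse NOAEL (Section 9.4.6). These points keep the matter minor; none supplies the scheduled reading.

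Finally, only part of the protocol file is available, so wording elsewhere or in a later amendment could already deal with this. That limit stands.

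**Conclusion.** The point holds for the Amendment 3 text shown, as a minor improvement. At any weight below about 133 kg, a Cohort 1 infusion ends before the first in-infusion reading can fall due, and no end-of-infusion reading is listed. At an assumed 50–110 kg the infusion lasts 3.75–8.25 minutes. One subject is affected if Subject 1 stays below 5 IU/dL in both assays at Week 3; otherwise normally up to four.

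This is a gap in scheduled readings, not an absence of monitoring. No endpoint, escalation rule or planned analysis depends on it. The conclusion rests on the stated concentration, rate and dose; body weight is the only assumed input.

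**What to change.** In Sections 9.4.4, 9.7.8.4 and 12.4, and in the matching Table 9.1.1 footnote, require a vital-sign reading at the end of infusion in all cohorts and state that the hourly series then starts at +1 h. This places the first post-start reading in Cohort 1 at about 4–8 minutes, covers Cohort 2 subjects under 60 kg, and settles the 0 h or +1 h question. Readings at 15 and 30 minutes after infusion are an optional addition.

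The cost is one clause in three sections and one footnote. It adds one Day 1 reading per subject to about 12 post-infusion readings already scheduled: at most 1 × 12 = 12 in the study, of which normally one to four are in Cohort 1. With both optional readings it is 3 × 12 = 36 at most.

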9.4.5 Method of Assigning Subjects to Treatment Groups

Subjects who meet all eligibility criteria (refer to Section 9.3.1 and Section 9.3.2) may be enrolled into the study. Approval by the Sponsor will be required prior to enrollment of each study subject. Upon their enrollment into the study, subjects will be assigned a unique subject number and dose level by the Sponsor.

Cohorts are enrolled serially and their dose is defined in Section 9.4.6.2 below. Escalation is based on FVIII activity 3 weeks after injection. Cohorts may receive the next higher dose if subjects in the previous cohort does not meet the activity criteria, or the same dose if subjects in the previous cohort meets the activity criteria.

9.4.6 Selection of Doses Used in the Study

The starting dose was based on the expression of hFVIII observed in nonclinical studies of mice and monkeys. The starting dose has a significant safety margin (10-fold) from NOAEL in mice. The dose escalation is half-logs based.

9.4.6.1 Selection of Timing of Dose for Each Subject

A minimum of three weeks are required between subjects, to allow for evaluation of safety and expression of hFVIII. After three weeks, depending on the activity level, the choice of the dose for the next subject will be made as described below.

9.4.6.2 Selection of Dose for Each Subject

The starting dose was determined by expression of hFVIII observed in mice and monkeys and a scale up factor based on previous experience, an improved purification process over previous trials (thus potentially decreasing the risk of immune response), and a new evaluation of the titer (PCR performed after hairpin removal).

Approximately three weeks after an injection, the decision to escalate to the next dose level will be made based on the review of safety parameters and FVIII activity by the Sponsor and the DRB.

Subject 1 (Cohort 1) will be dosed by intravenous infusion with 6E12 vg/kg of body weight. If the FVIII activity level does not reach 5 IU/dL or greater (expressed as % in Figure 9.1.1) at the Week 3 visit in both assays, then no further subjects will be dosed in Cohort 1 and enrollment into Cohort 2 will initiate with Subject 2 at the next dose (2E13 vg/kg).

If the FVIII activity level in the first subject treated in Cohort 2 does not reach \geq 5 IU/dL at the Week 3 visit in both assays, then no further subjects will be dosed in Cohort 2 and enrollment into Cohort 3 (6E13) will initiate with the next subject.

If the FVIII activity level in the first subject treated in Cohort 3 does not reach \geq 5 IU/dL at the Week 3 visit in both assays, then the DRB will recommend whether to continue to add subjects to the cohort and/or whether to continue the study.

For the first subject treated in each Cohort, if the activity level reaches \geq 5 IU/dL and no safety issue is found, then up to four subjects will be enrolled in the Cohort. Although the optimum design of this study is three cohorts of 4 subjects, the adaptive nature of this trial allows the DRB to recommend allocating subjects to the cohorts based on activity levels of FVIII and safety signals.

Refer to Figure 9.1.1 for a visual representation of the study design.

9.4.7 Blinding

This is an open-label study.

9.4.8 Prior and Concomitant Medications

All prescription and over-the-counter medications taken by a subject for 30 days before Screening will be recorded on the designated CRF. The Investigator may prescribe additional medications during the study, as long as the prescribed medication is not prohibited by the protocol. In the event of an emergency, any needed medications may be prescribed without prior approval, but the medical monitor must be notified of the use of any contraindicated medications immediately thereafter. Any concomitant medications added or discontinued during the study should be recorded on the CRF.

The following medications are prohibited starting 30 days before Screening:

- Live vaccines
- Systemic immunosuppressive agents

9.4.8.1 Concomitant Haemophilia Treatments

Subjects on "on demand" therapy for FVIII will continue their treatment at will. Subjects on prophylactic FVIII therapy will discontinue their treatment starting the day of infusion and switch to an "on demand" schedule. FVIII can always be taken as needed by the subject, who will carefully record his treatment and bleeding episodes in his diary.

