9.7.3 Secondary Efficacy Variables

Secondary efficacy measures will be the reduction in the frequency of factor replacement therapy, and reduction in the number of bleeding episodes. Subjects will be asked at each study visit to report the use of factor replacement therapy and the number of bleeding episodes since the previous visit. This information will be captured on the subject's diary or other subject records.

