Treatment of severe HA presently consists of intravenous injection of plasma derived or recombinant FVIII protein (rhFVIII) concentrates both as prophylaxis 2-3 times per week, and at the time of a bleed, to prevent or control bleeding episodes, respectively. The half-life for rhFVIII (under 24 hours for most approved products) necessitates frequent infusions, and although a major advance in the treatment of HA, it remains common for severe HA patients to continue to have multiple bleeding events on treatment (mean of 1 to 7 episodes/year with prophylaxis up to 30 to 50 for on demand treatment). The consequence of multiple bleeding events is the development of an underlying pathology that contributes to debilitating multiple-joint arthropathy and substantially increased risk of death. Chemical modification (e.g. direct conjugation of polyethylene glycol (PEG) polymers) and bioengineering of FVIII (e.g. FVIII-Fc fusion proteins) improve half-life by approximately 50%, and

[figure not shown]
BOMARIN [®] 270-	201- Amendment 2	Page 5
NAME OF COMPANY	SUMMARY TABLE	FOR NATIONAL
BioMarin Pharmaceutical Inc.	Referring to Part of the	AUTHORITY USE
[name]	Dossier:	ONLY:
[name]		
	Volume:	
NAME OF FINISHED PRODUCT:		
BMN 270	Page:	
NAME OF ACTIVE INGREDIENT: AAV5-hFVIII-SQ	Reference:	

[figure not shown]
thus, show promise in reduced dosing and maintaining activity levels above 1% trough. However, these longer acting FVIIIs remain dependent on multiple infusions to maintain critical levels of FVIII activity in severe HA patients. There is therefore a strong unmet need for a fully preventive treatment of HA to give patients a FVIII level compatible with a normal and haemorrhage-free life.

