8 STUDY OBJECTIVES

The primary objectives of the study are:

- To assess the safety of a single intravenous administration of a recombinant AAV5 encoding human coagulation FVIII (AAV5-hFVIII-SQ) vector.
- To determine the dose of AAV5-hFVIII-SQ required to achieve expression of hFVIII at or above 5% of normal activity (≥5 IU/dL) at 16 weeks after infusion. The kinetics, duration and magnitude of AAV-mediated hFVIII activity in individuals with haemophilia A will be determined and correlated to an appropriate BMN 270 dose.

The secondary objectives of the study are:

- To describe the immune response to the hFVIII transgene product and AAV capsid proteins following systemic administration of AAV5-hFVIII-SQ
- To assess the impact of BMN 270 on the frequency of FVIII replacement therapy during the study
- To assess the impact of BMN 270 on the number of bleeding episodes requiring treatment during the study

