9.2 Discussion of Study Design, Including Choice of Control Group

Study 270-201 is designed to be a first-in-man, phase 1/2 open-label, dose escalation study in patients with severe haemophilia A. Three doses of BMN 270 will be evaluated and the dose escalation decision tree is summarized in Figure 9.1.1.

The decision to escalate to the next dose level will be made based on the review of safety parameters and FVIII activity by the Sponsor and a panel of investigators participating in the study.

There will be no control group. Parameters for each patient will be compared to a pre-treatment assessment of safety (liver function) and efficacy (number of bleeds, use of replacement therapy).

As AAV based treatment always leads to anti-capsid immune response, no true control group (for example with an empty AAV) is possible.

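### Stopping prophylaxis on the infusion day can lower FVIII use by itself, so the before-and-after secondary measure does not isolate an effect of BMN 270 in prior-prophylaxis subjects

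*Protocol*

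**What the plan says.** Section 9.4.8.1 fixes the background regimen after dosing: "Subjects on prophylactic FVIII therapy will discontinue their treatment starting the day of infusion and switch to an" on-demand schedule. Subjects already on demand carry on as before. After dosing, "FVIII can always be taken as needed by the subject, who will carefully record his treatment and bleeding episodes in his diary".

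Section 9.7.3 defines the measures: "Secondary efficacy measures will be the reduction in the frequency of factor replacement therapy, and reduction in the number of bleeding episodes". Section 9.2 names the comparator: "Parameters for each patient will be compared to a pre-treatment assessment of safety (liver function) and efficacy (number of bleeds, use of replacement therapy"). The same section states that there is no control group.

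Section 8 phrases the aims as the impact of BMN 270, first on the frequency of FVIII replacement and then on bleeds: "To assess the impact of BMN 270 on the number of bleeding episodes requiring treatment during the study". Section 9.7.3 counts bleeding episodes without that restriction.

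Section 14.2 makes the analysis descriptive. It summarises efficacy variables by dose cohort at each time point and has the relationship between dose and efficacy examined. Section 9.3.1 admits both prior regimens; its minimum of 12 bleeds in the past year applies only to on-demand patients. Nothing in the text shown splits these measures by prior regimen.

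On versions: Sections 9.4.8.1, 9.7.3 and 14.2 are read in Amendment 3. Sections 8, 9.2 and 9.3.1 and the Synopsis are read in Amendment 2, because those parts of Amendment 3 are not in the text at hand. The Amendment 3 change log retains the comparison in 9.2 and the bleed rates, and lists no change to Section 8.

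**The concern.** Each subject is his own control, yet in prior-prophylaxis subjects two things change on the same day: the vector is given and the scheduled infusions stop. The count before dosing includes scheduled infusions. The count after dosing is meant to contain only on-demand ones. The measured quantity is thus altered by instruction at the moment of treatment, and no concurrent group shows what the instruction alone would do.

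The bleed count in the same subjects is disturbed in the other direction, because protection has been withdrawn. Two of the three secondary objectives rest on these counts. With cohorts of up to four subjects (Section 9.4.6.2), the mix of prior regimens could imitate or hide a relationship with dose.

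**Working it through.** The protocol gives no expected value for this measure, so there is no figure to reproduce. The check is what a vector with no effect would show.

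**Inputs**
- Scheduled infusions, w: the Synopsis describes "concentrates both as prophylaxis 2-3 times per week", so w = 2 to 3 per week.
- Bleeds per year on prophylaxis (b) and on demand (B): "mean of 1 to 7 episodes/year with prophylaxis up to 30 to 50 for on demand treatment". So b = 1 to 7, and B = 30 to 50 as upper figures.
- Infusions per bleed, k: not in the protocol, so assumed and ranged from 1 to 7.

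**Scheduled infusions removed**

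2 × 52 = 104 and 3 × 52 = 156 a year. Over the 16-week follow-up this is 2 × 16 = 32 to 3 × 16 = 48.

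**Total infusions per year with no drug effect**

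Before = 52w + bk. After = Bk. Change = After/Before − 1. Taking both ends of w, b and B gives eight combinations. The largest fall is at w = 3, b = 7, B = 30. The smallest fall, or largest rise, is at w = 2, b = 1, B = 50.

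| k | Most favourable to a fall | Least favourable to a fall | Combinations with a fall |
|---|---|---|---|
| 1 | 163 to 30: -82% | 105 to 50: -52% | 8 of 8 |
| 2 | 170 to 60: -65% | 106 to 100: -6% | 8 of 8 |
| 3 | 177 to 90: -49% | 107 to 150: +40% | 6 of 8 |
| 4 | 184 to 120: -35% | 108 to 200: +85% | 3 of 8 |
| 7 | 205 to 210: +2% | 111 to 350: +215% | 0 of 8 |

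**Break-even**

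Setting Before = After gives k = 52w/(B − b). The lowest value is 104/(50 − 1) = 2.1 and the highest is 156/(30 − 7) = 6.8. Below 2.1 infusions per bleed every combination shows a fall; above 6.8 none does. B is an upper figure, and fewer on-demand bleeds raise the break-even. The Amendment 3 log entry for Section 7.3 is garbled and may give up to 4 infusions a week. At 4 × 52 = 208 a year the break-even runs from 208/49 = 4.2 to 208/23 = 9.0, which makes an apparent fall more likely.

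**Bleeds under the same switch**

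From 1–7 to as many as 30–50 a year. The smallest ratio is 30/7 = 4.3.

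**Case mix, as an illustration**

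Take w = 3, b = 7, B = 30, k = 2 and no drug effect. Each prior-prophylaxis subject changes by 60 − 170 = -110 infusions and 30 − 7 = +23 bleeds a year. On-demand subjects are taken as unchanged. A cohort of four with three prior-prophylaxis subjects shows mean changes of 3 × (-110)/4 = -82.5 infusions and 3 × 23/4 = +17.25 bleeds. With one such subject the means are -27.5 and +5.75. The two cohorts differ in prior regimen only.

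**The case against.** The strongest reply is that the protocol claims little here. Section 14.2 is descriptive and no threshold or test attaches to Section 9.7.3. A reader might infer that the measure is met in prophylaxis subjects even if BMN 270 does nothing. The documents do not support that: there is no criterion to meet, and FVIII may be taken as needed, so above about 2.1 infusions per bleed the protocol's own ranges allow use to rise. This stands and limits the point.

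Second, bleeds are listed beside FVIII use and both are collected throughout. A vector with no effect would tend to raise bleeds in exactly these subjects, so the pair read together would partly expose it. That also stands, but it works only if the two are read together within prior regimen, which the text does not ask for.

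Third, table breakdowns are often left to the SAP, and Section 14.8 lets the SAP prevail. But the protocol itself fixes the measure, its comparator, its description as an impact of BMN 270 and the summary by dose cohort. A breakdown by regimen is not excluded; the attribution is what needs correcting.

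A reader might also infer that on-demand subjects, selected for at least 12 bleeds, will improve by regression to the mean. The protocol gives nothing to size this, and 12 lies well below its own on-demand figure of up to 30 to 50, so it carries no weight here.

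Finally, the primary aims and dose escalation rest on safety and assayed FVIII activity, not infusion counts. This stands and lowers the severity.

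**Conclusion.** In prior-prophylaxis subjects, the change in frequency of factor replacement mixes a protocol instruction with any drug effect and cannot separate them. The switch alone removes 104 to 156 scheduled infusions a year. With no drug effect, total use falls in every combination of the protocol's figures at one or two infusions per bleed; at three or more the direction depends on the inputs. The result rests on the Synopsis rates and on the assumed infusions per bleed. The number of prior-prophylaxis subjects is not stated, so the effect on any one table is unknown.

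Bleeds are biased the other way in the same subjects, so mixed-regimen cohort summaries of either measure reflect case mix as well as dose. Separately, Section 8 counts treated bleeds and Section 9.7.3 all bleeds. Severity is moderate.

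**What to change.** In Sections 9.7.3 and 14.2:

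- Report FVIII use and bleeds separately for prior-prophylaxis and prior on-demand subjects.
- In prior-prophylaxis subjects, separate scheduled from bleed-treating infusions, and state that the fall in total infusion frequency is not attributed to BMN 270.
- For these subjects, show post-dose treated bleeds and bleed-treating infusions beside the bleed rate on prophylaxis.
- Use one bleed definition in Sections 8 and 9.7.3.

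The cost is wording and a split table. Bleeds and FVIII use are already documented at screening and baseline (Sections 12.2 and 12.3) and in the diary after dosing, and eligibility already requires the prior regimen to be known. The downside is smaller subgroups in secondary tables that are already small. No treatment rule changes.
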